#### **10.4 Telephone Follow-up (Phone Follow-Up, D1)**

The participant will be contacted by telephone to check on the overall response to the infusion. This will include the DSQ-PEM instrument administered over the phone to assess post-exertional symptoms.

#### **10.5 Follow-up Visits (D15, D30, D90, D180, D360)**

In-person follow-up visits will occur as outlined in the Schedule of Events. At each visit, vital signs will be collected, and the participant will undergo a targeted physical assessment as needed. They will complete clinical assessments as outlined in the Schedule of Events. Laboratory tests will be ordered and biospecimens collected and stored for later testing as per the Schedule of Events.

#### **10.6 Unscheduled (Interim) Visits**

An unscheduled (or interim) visit is defined as any visit not pre-specified in the study protocol. An unscheduled visit may be scheduled in order to assess a participant in person, repeat a laboratory test, or to collect additional biospecimens at the discretion of the PI.

#### **10.7 Study Discontinuation Visit**

If a subject withdraws or discontinues from the study, they should complete a Study Discontinuation Visit. If D0 has occurred, this visit should at a minimum include AE assessment and documentation of the reason for discontinuation or withdrawal. Whenever possible, the study events for the Study Discontinuation Visit should be as follows:

- Prior to D0: No further assessment needed.
- Between D0 and D15: Complete D15 assessments.
- After D15: Complete D90 assessments (even if D90 has elapsed).

### **11 ADVERSE EXPERIENCE REPORTING AND DOCUMENTATION**

#### **11.1 Adverse Events**

An adverse event (AE) is any untoward medical occurrence in a clinical investigation of a patient administered a pharmaceutical product, which does not necessarily have a causal relationship with the treatment. An AE is therefore any unfavorable and unintended sign (including an abnormal laboratory finding), symptom or disease temporally associated with the administration of an investigational product, whether or not related to that investigational product. An unexpected AE is one of a type not identified in nature, severity, or frequency in the current Investigator's Brochure or of greater severity or frequency than expected based on the information in the Investigator's Brochure.

**Suspected Adverse Reaction (SAR)** - any AE for which there is a reasonable possibility that the drug caused it. It implies a lesser degree of certainty about causality than **adverse reaction** (any AE caused by a drug).

An unexpected AE or unexpected SAR is one of a type not identified in nature, severity, or frequency in the current Investigator's Brochure or of greater severity or frequency than expected based on the information in the Investigator's Brochure.

The Investigator will probe, via discussion with the subject, for the occurrence of AEs during each subject visit and record the information in the site's source documents. Adverse events will be recorded in the patient CRF. Adverse events will be described by duration (start and stop dates and times), severity, outcome, treatment and relation to study drug, or if unrelated, the cause.

### 11.1.1 AE Severity

Except for infusion-related site reactions, the National Institutes of Health Division of AIDS (DAIDS) Table for Grading the Severity of Adult and Pediatric Adverse Events, Corrected Version 2.1 (July 2017) should be used to assess and grade AE severity, including laboratory abnormalities judged to be clinically significant. The modified criteria can be found in the study manual. If the experience is not covered in the modified criteria, the guidelines shown in Table 2 below should be used to grade severity. It should be pointed out that the term "severe" is a measure of intensity and that a severe AE is not necessarily serious. Infusion-related site reactions will be graded according to protocol section 9.1.8.

**Table 2. AE Severity Grading**

Severity (Toxicity Grade)	Description
Mild (1)	Transient or mild discomfort; no limitation in activity; no medical intervention or therapy required. The subject may be aware of the sign or symptom but tolerates it reasonably well.
Moderate (2)	Mild to moderate limitation in activity, no or minimal medical intervention/therapy required.
Severe (3)	Marked limitation in activity, medical intervention/therapy required, hospitalizations possible.
Life-threatening (4)	The subject is at risk of death due to the adverse experience as it occurred. This does not refer to an experience that hypothetically might have caused death if it were more severe.

### 11.1.2 AE Relationship to Study Drug

The relationship of an AE to the study drug should be assessed using the following the guidelines in Table 3 below.

**Table 3. AE Relationship to Study Drug**

Relationship to Drug	Comment
Definitely	Previously known toxicity of agent; or an event that follows a reasonable temporal sequence from administration of the drug; that follows a known or expected response pattern to the suspected drug; that is confirmed by stopping or reducing the dosage of the drug; and that is not explained by any other reasonable hypothesis.

Probably	An event that follows a reasonable temporal sequence from administration of the drug; that follows a known or expected response pattern to the suspected drug; that is confirmed by stopping or reducing the dosage of the drug; and that is unlikely to be explained by the known characteristics of the subject's clinical state or by other interventions.
Possibly	An event that follows a reasonable temporal sequence from administration of the drug; that follows a known or expected response pattern to that suspected drug; but that could readily have been produced by a number of other factors.
Unrelated	An event that can be determined with certainty to have no relationship to the study drug.

## 11.2 Serious Adverse Experiences (SAE) or Serious SAR

An SAE is defined as any AE occurring at any dose that results in any of the following outcomes:

- death
- a life-threatening adverse experience
- inpatient hospitalization or prolongation of existing hospitalization
- a persistent or significant disability/incapacity
- a congenital anomaly/birth defect

Other important medical events may also be considered an SAE when, based on appropriate medical judgment, they jeopardize the subject or require intervention to prevent one of the outcomes listed.

A **life-threatening AE or life-threatening SAR** is an occurrence that places the patient or subject at immediate risk of death. It does NOT include an AE or SAR that, had it occurred in a more severe form, might have caused death.

**SUSARS** are fatal or life threatening serious unexpected SARs. The team must notify the FDA as soon as possible, but no later than 7 calendar days after the initial receipt of information.

[figure not shown]
### 11.2.1 Serious Adverse Experience Reporting

Study sites will document all SAEs that occur (whether or not related to study drug) per [UCSF CHR Guidelines](#). The collection period for all SAEs will begin after informed consent is obtained and end after procedures for the final study visit have been completed.

In accordance with the standard operating procedures and policies of the local Institutional Review Board (IRB)/Independent Ethics Committee (IEC), the site investigator will report SAEs to the IRB/IEC.

Aerium Therapeutics, the manufacturer of the IP, shall be notified within 24 hours of PI awareness of an SAE. In addition, an AE master list shall be sent to Aerium Therapeutics monthly.

#### FDA IND Expedited Safety reporting Requirements

Additional FDA IND 15-day expedited reporting includes new safety findings from other clinical trials, findings from in vitro and animal testing, and increased rate of occurrence of serious SARS.

## 12 DISCONTINUATION AND REPLACEMENT OF SUBJECTS

### 12.1 Early Discontinuation

A subject may be discontinued from study treatment at any time if the subject or the investigator feels that it is not in the subject's best interest to continue. The following is a list of possible reasons for study treatment discontinuation:

- Subject withdrawal of consent
- Subject is not compliant with study procedures
- Adverse event that in the opinion of the investigator would be in the best interest of the subject to discontinue study treatment
- Protocol violation requiring discontinuation of study treatment
- Lost to follow-up
- Manufacturer request for early termination of study

If a subject is withdrawn from treatment due to an adverse event, the subject will be followed and treated by the Investigator until the abnormal parameter or symptom has resolved or stabilized.

All subjects who discontinue study treatment should come in for an early discontinuation visit (as outlined above) as soon as possible and then should be encouraged to complete all remaining scheduled visits and procedures.

All subjects are free to withdraw from participation at any time, for any reason, specified or unspecified, and without prejudice.

Reasonable attempts will be made by the investigator to provide a reason for subject withdrawals. The reason for the subject's withdrawal from the study will be specified in the subject's source documents. Refer to Section 10 for study discontinuation procedures.

## **12.2 Withdrawal of Subjects from the Study**

A subject may be withdrawn from the study at any time if the subject or the investigator feels that it is not in the subject's best interest to continue.

All subjects are free to withdraw from participation at any time, for any reason, specified or unspecified, and without prejudice.

Reasonable attempts will be made by the investigator to provide a reason for subject withdrawals. The reason for the subject's withdrawal from the study will be specified in the subject's source documents. As noted above, subjects who discontinue study treatment early (i.e., they withdraw prior to D360) should have an early discontinuation visit. Refer to Section 10 for early termination procedures.

## **12.3 Replacement of Subjects**

Subjects who withdraw from the study prior will be replaced at the discretion of the investigator.

## **12.4 Lost to Follow Up**

A subject will be considered LTFU if s/he repeatedly fails to return for scheduled visits and is unable to be contacted by the study site. The following actions must be taken if a subject fails to return to the clinic for a required study visit:

- The site must attempt to contact the subject and reschedule the missed visit as soon as possible, counsel the subject on the importance of maintaining the assigned visit schedule and ascertain whether the subject wishes to and/or should continue in the study.
- Before a subject is deemed LTFU, the investigator or designee must make every effort to regain contact with the subject (at a minimum, 2 telephone calls and, if necessary, a certified letter to the subject's last known mailing address or local equivalent methods). These contact attempts should be documented in the subject's source documents.

Should the subject continue to be unreachable, s/he will be considered to have withdrawn from the study.

## **13 PROTOCOL VIOLATIONS**

A protocol violation occurs when the subject or investigator fails to adhere to significant protocol requirements affecting the inclusion, exclusion, subject safety, and primary endpoint criteria. Protocol violations for this study include, but are not limited to, the following:

- Failure to meet inclusion/exclusion criteria
- Use of a prohibited concomitant medication

Failure to comply with Good Clinical Practice (GCP) guidelines will also result in a protocol violation. The Investigator will determine if a protocol violation results in withdrawal of a subject.

When a protocol violation occurs, it will be discussed with the investigator and a Protocol Violation Form detailing the violation will be generated. This form will be signed by the Investigator or delegate. A copy of the form will be filed in the site's regulatory binder and in the Investigator's files.

## **14 DATA SAFETY MONITORING**

The Investigator will establish a Safety Monitoring Committee (SMC) to review data relating to safety, and to ensure the continued scientific validity and merit of the study, according to SMC Charter to be established for this protocol.

Scheduled SMC meetings will occur as outlined in the SMC Charter, approximately 3 times per year (generally about 4 months after the first participant is enrolled, and about every 4 months thereafter). The SMC will meet and review accrual (including screening and enrollment), AE summaries, including all reported Grade  $\geq 3$  AEs, retention of participants including off-study rates.

In addition, after 10 individuals have been dosed, the study will pause for further dosing (follow up will still occur) for a blinded SMC review of the 2-week safety data on the first 10 enrollees to ensure that no safety concerns warranting altering or stopping the study are identified; this may take place as part of a regular SMC meeting or an ad hoc meeting depending on timing.

In addition to the regularly scheduled reviews, a safety review will be conducted by the SMC for any of the following criteria:

- Two or more participants experience an SAE that is deemed possibly, probably, or definitely related to the study treatment.
- One or more participants experience a Grade 4 AE that is deemed possibly, probably, or definitely related to the study treatment.

If the above criteria are met, the PI will request a review by the SMC (or the SMC chair if other SMC members cannot be convened), to be held within 3 business days of learning of the event.

Whenever any of the events above occurs, enrollment into the study will be paused until the SMC review has taken place and a determination has been made that enrollment can resume. In addition, administration of study products will be paused until a course of action is recommended by the SMC. Follow-up visits (Baseline Assessments, D1, W2, M1, M3, M6, and M12, and unscheduled visits) can continue during this period of review as these are not expected to affect the safety of participants who have already received the study IP.

The SMC will recommend, based on the results of the review, whether the study can proceed as planned, proceed with modifications, or should be discontinued.

The SMC will review progress towards pre-specified benchmarks of enrollment and retention of participants, completion of study procedures, and collection of viable samples. If progress towards any benchmark is not adequate, as determined by the SMC, the SMC will recommend protocol modification if necessary.

## **15 STATISTICAL METHODS AND CONSIDERATIONS**

Prior to the analysis of the final study data, a detailed Statistical Analysis Plan (SAP) will be written describing all analyses that will be performed. The SAP will contain any modifications to the analysis plan described below.

### **15.1 Data Sets Analyzed**

Eligible patients who are randomized into the study and receive the study drug will comprise the modified intent to treat (mITT) population and will be the primary analysis population for all analyses.

Per protocol analysis will be based on description of the results per study group excluding anyone who has received a non-study COVID-neutralizing mAb during the trial period, anyone with resistant SARS-CoV-2 infections during the trial or receipt of COVID antivirals during the trial.

## **15.2 Demographic and Baseline Characteristics**

The following demographic variables at screening will be summarized by dose level: race, gender, age, height, and weight.

## **15.3 Analysis of Primary Endpoint**

Safety and tolerability data will be summarized by treatment group.

Adverse event rates will be coded by body system. Adverse events will be tabulated by treatment group and will include the number of patients for whom the event occurred, the rate of occurrence, and the severity and relationship to study drug. Adverse events between groups will be summarized by proportions with associated 95% Clopper-Pearson confidence intervals and will be compared using a two-sided 0.05 level Fisher exact test.

## **15.4 Analysis of Secondary Endpoints**

The key secondary outcome will be the change in the PROMIS-29 score from baseline to D90. This will be analyzed from the mITT population using a linear regression model for follow-up PROMIS-29 with terms for the baseline value, randomized treatment and randomization strata (<6 months v.  $\geq$  6 months of symptoms) – an analysis of covariance model (ANCOVA) and tested using a two-sided 0.05 level test.

Continuous secondary events (e.g., IL-6) will be compared using the ANCOVA approach. Antigen detection will be summarized by proportion with 95% Clopper-Pearson confidence intervals and will be compared using a two-sided 0.05 level Fisher exact test.

As above, eligibility is determined by Long COVID attributed to a SARS-CoV-2 infection prior to August 15, 2022. All participants will be required to have Long COVID attributed to an infection prior to this date. A sub-analysis will address individuals with and without a known history of SARS-CoV-2 re-infection after August 15, 2022.

## **15.5 Interim Analysis**

Interim analysis of group level results without subject level unblinding will be conducted for all subjects reaching 3M.

## **15.6 Sample Size and Randomization**

This is an exploratory study, and the primary results will be descriptive. We will use AER002 as a probe to better understand LC biology and determine whether a signal is present to warrant further study.

The study will enroll 30 participants who meet the WHO LC criteria. Participants will be enrolled at a single center and randomized 2:1 to receive AER002 1200mg or placebo. Randomization will be stratified by duration of infection (<6 months and  $\geq$  6 months) at Day 0.

For PROMIS-29, assuming a standard deviation (SD) of the within-person difference of 10, then the planned sample size will have 80% power to detect a difference of 11.2 on a two-sided 0.05 level test.

For biomarkers, such as IL-6, we will be able to detect a difference from a mean value of 2.5 pg/mL to 1.1 times the within-person standard deviation with 80% power.

We assume that 25% of participants will have positive antigen at entry, we will have 62% power to detect a reduction to < 1% with positive antigen on the treatment arm.

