## 8 STUDY TREATMENTS

### 8.1 Method of Assigning Subjects to Treatment Groups

The 30 participants will be randomized, 20 to AER002 and 10 to placebo. The randomization will be stratified by duration of COVID-19 related symptoms (< 6 months vs. ≥ 6 months). Within the strata, randomization will use permuted blocks of 3 and 6 enrollees with equal likelihood.

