### **3.3. Binary outcomes**

For binary outcomes, probabilities will be compared between the investigational agent and its control group using Fisher's exact tests or logistic regression. Proportions will be accompanied by Agresti Coull 95% confidence intervals. Relative risks will be calculated with 2-sided 95% confidence intervals. Risk difference (RD) with 2-sided 95% confidence intervals (CI) will also be compared between the groups. If the numbers in the denominators are small, our confidence intervals will use the pseudo-observation approach of Agresti and Caffo.

For longitudinally measured binary outcomes, the treatment effect, in relative risks, through follow-up will be estimated with 95% confidence intervals using generalized estimating equations (GEE) with a Poisson family and a log link function; the treatment effect is estimated via the interaction between the indicator for randomization group and the binary indicator for follow-up (versus baseline) visits. Here, we may also employ the pseudo-observation approach to calculating the confidence intervals if the outcomes are rare. The treatment effect, in risk differences, with 95% confidence intervals will be estimated by marginalizing the models and calculating 95% confidence intervals by the chain rule.

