#### **4.3.3 Laboratory Measures**

- Change from Baseline to D15, D30, and D180 in CRP, ESR, D-Dimer, and Fibrinogen
  - The primary estimand for these outcomes is the difference in mean change from baseline.
  - These continuous outcomes will be analyzed as described in [Section 3.5](#) , i.e. using a mixed effect model for repeated measurements.
- Percentage of participants with no detection of SARS-CoV-2 plasma remnants (i.e., viral detection by reverse transcriptase-polymerase chain reaction (RT-PCR) and Spike protein fragments) compared to Baseline through D180.

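### Protocol 15.6 claims 62% power for antigen clearance, but the Fisher exact test named in 15.4 gives about 43% to 47% with 20 versus 10 participants if placebo positivity stays at 25%

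*Combined protocol and SAP*

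**What the plan says.** Protocol section 15.6 bases its antigen statement on one rate: "We assume that 25% of participants will have positive antigen at entry". It then says that "we will have 62% power to detect a reduction to < 1% with positive antigen on the treatment arm". It names no test for this calculation and gives no positivity rate for placebo participants at follow-up.

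The design inputs are elsewhere in the protocol. Section 8.1: "The 30 participants will be randomized, 20 to AER002 and 10 to placebo". Section 15.4, on antigen detection: the proportions "will be compared using a two-sided 0.05 level Fisher exact test".

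The later SAP does not repeat the antigen power figure. Its section 2.4 carries over only the PROMIS-29 and IL-6 statements. Section 3.3 compares binary outcomes by Fisher's "exact tests or logistic regression", with a separate GEE approach for longitudinal binary outcomes. Section 4.3.3 lists "Percentage of participants with no detection of SARS-CoV-2 plasma remnants" among the exploratory laboratory measures.

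**The concern.** Ten placebo participants at 25% positivity means 2.5 expected positives. At counts this small an exact test can have much lower power than a large-sample formula suggests, so 62% looked too high for the test the protocol names.

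What is at stake is how a non-significant antigen result is read. Effect on virologic markers is the first secondary objective in protocol 3.2, and 15.6 says the trial is meant to show whether there is a signal worth pursuing. A reader who believes 62% would think that near-complete clearance had a better than even chance of being detected. If the true figure is below 50%, missing real clearance is the likelier outcome.

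**Working it through.** **Inputs**

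- Arm sizes: 20 AER002, 10 placebo (protocol 8.1).
- Treatment rate: below 1%, so 0% to 1% (protocol 15.6).
- Test: Fisher exact, two-sided, 0.05 (protocol 15.4).
- Placebo rate at follow-up: 25%. This is an assumption, carrying the entry rate in 15.6 forward because no other comparator rate is given.
- All 30 participants contribute data (assumption).

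**Step 1. Where 62% comes from.** Take the uncorrected normal approximation, with the pooled standard error under the null:

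power = Φ{ [(p_c − p_t) − 1.96·√(p̄(1 − p̄)(1/10 + 1/20))] / √(p_c(1 − p_c)/10 + p_t(1 − p_t)/20) }

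- At 25% vs 0%, p̄ = 2.5/30 = 0.0833. The pooled SE is 0.1070 and the unpooled SE is 0.1369. (0.25 − 1.96 × 0.1070)/0.1369 = 0.294, and Φ(0.294) = **61.5%**.
- At 25% vs 1%, p̄ = 0.09, the SEs are 0.1108 and 0.1387, the argument is 0.164 and power is **56.5%**.

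So 62% is reproducible, but from a large-sample formula with essentially nobody positive on AER002. An arcsine approximation also passes through 62%, between 0.5% (64.7%) and 1% (59.0%) on treatment. Neither is the test in 15.4.

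**Step 2. When Fisher rejects.** Enumerating all 21 × 11 tables gives this boundary:

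| AER002 positives (of 20) | Placebo positives needed (of 10) | p at the boundary | p one count below |
|---|---|---|---|
| 0 | 3 | 0.030 | 0.103 |
| 1 | 4 | 0.031 | 0.095 |
| 2 | 5 | 0.026 | 0.141 |

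**Step 3. Power at 25% vs 0%.** Rejection needs at least 3 of 10 placebo positives:

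1 − (0.0563 + 0.1877 + 0.2816) = **47.4%**

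This is the maximum for any treatment rate below 1%.

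**Step 4. Power at 25% vs 1%.** Weight each boundary by the chance of 0, 1 or 2 positives among 20 on AER002:

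0.8179 × 0.4744 + 0.1652 × 0.2241 + 0.0159 × 0.0781 = 0.3880 + 0.0370 + 0.0012 = **42.6%**

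Higher AER002 counts add a negligible amount.

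**Step 5. Sensitivity to the unstated placebo rate (Fisher)**

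| Placebo positivity at follow-up | Power, 1% on AER002 | Power, 0% on AER002 |
|---|---|---|
| 20% | 28.4% | 32.2% |
| 25% | 42.6% | 47.4% |
| 30% | 56.5% | 61.7% |
| 35% | 68.8% | 73.8% |
| 25%, only 9 placebo evaluable | 35.5% | 39.9% |

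Fisher reaches 62% at a placebo rate of about 30.1% (0% on treatment) to 32.1% (1% on treatment).

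**Step 6. The logistic option in SAP 3.3.** For an unadjusted two-group model at 25%, the likelihood-ratio test rejects with probability 65.7% (1%) to 75.6% (0%), but its actual type I error reaches 7.0%, at a common rate of about 22%. The Wald test rejects with probability 3.8% or less, counting tables with a zero cell as non-significant. Neither supports 62% at a true 5% level. The GEE option was not computed.

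**The case against.** The strongest reply has four parts.

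*The 62% is not a slip, and 25% is an entry rate.* The figure follows from a standard planning formula, and 15.6 names no test for it. Holding placebo at 25% is an added assumption. The protocol endpoint covers 1 to 6 months after dosing, and section 2 describes antigen as intermittently detectable. Read cumulatively, placebo detection could exceed 25%, and at 30% to 35% Fisher power is 57% to 74%. This stands as a limit on the claim: the gap is a mismatch between planning method and named test, and its size is conditional. But 25% is the only rate the protocol offers, and a lower placebo rate or a lost placebo participant would widen the gap.

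*The SAP has moved on.* It drops the figure, makes the endpoint exploratory and permits other methods. All true, and this limits the consequence. The sentence nevertheless remains in the protocol, whose own section 15.4 names only Fisher for antigen detection.

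*Nothing depends on the number.* Correct for sample size, the primary safety analysis and every planned analysis. Even 62% openly concedes modest power. What remains is the reading of a null result, and for that it matters whether the chance of detection is above or below one half.

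*Correcting it means a protocol amendment.* Also true. Protocol 17.1 requires prior written IRB/IEC approval for an amendment, so the administrative cost is more than the typing of a sentence.

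**Conclusion.** The stated power is wrong for the test and allocation the protocol specifies. With 20 versus 10, a two-sided 0.05 Fisher exact test, placebo positivity of 25% at follow-up and complete data, power is 42.6% at 1% on AER002 and at most 47.4% at 0%. The overstatement is 14.6 points (62 − 47.4) to 19.4 points (62 − 42.6).

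The conclusion rests on the placebo rate. It would disappear if that rate were about 30% to 32%, which the protocol does not state, and it worsens below 25%. The point deserves correction, but its reach is one sentence about an endpoint that the SAP treats as exploratory.

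**What to change.** Replace the antigen sentence in protocol 15.6 with wording to this effect:

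> Assuming that placebo positivity remains 25% at follow-up, with 20 AER002 and 10 placebo participants and a two-sided 0.05 Fisher exact test, power is about 43% for 25% versus 1% and at most 47% for 25% versus 0%.

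If the sponsor had a different placebo rate in mind, for example because detection is counted over several visits, 15.6 should state that rate and give the Fisher power that follows from it.

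The cost is a less favourable stated power and the approval step for a one-sentence amendment. No analysis, sample size or SAP text changes. SAP 2.4 needs no addition, and the planned proportions with confidence intervals already give the reader a direct view of the precision.
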